## 3.2.2.6 Figures on Efficacy Endpoints

Figures will show the LS means and 95% CIs for each treatment group, at each scheduled assessment up to Week 16, for MAS, PGA, GAS, CCI

and each PedsQL score. Forest plots of effect size by subgroups (Section 3.2.2.7) will also be provided for the primary efficacy endpoint. Histograms will present the number and percent of subjects within each MAS change category and within each PGA response category at Week 6 by treatment group.

3.2.2.7 Subgroup Efficacy Analyses and Covariates

Covariates used in models of efficacy analysis will be the same as those mentioned in sections 3.1.1 and 3.1.2.

The model will be run including the centre effect, which will be removed if the model does not converge.

The following additional subgroup analyses will be conducted on the MAS and the PGA of the mITT population:

Primary (MAS) and First Secondary (PGA) Efficacy Endpoint

- Age group (2 to 9 years and 10 to 17 years)
- BTX status at baseline (naïve or non-naïve)
- Sex (Male or Female).

MAS and PGA at Treatment Cycle 1 Week 16

• Physiotherapy/Occupational therapy status at Week 16 (No/Yes): Subjects without physiotherapy nor occupational therapy before week 16 of Treatment Cycle 1 versus subjects with physiotherapy and/or Occupational therapy between Baseline and Week 16 of Treatment Cycle 1.

Statistical analyses will include:

- A summary table of raw values and changes from baseline to all visits, by treatment group and overall, in each subgroup separately.
- A rank ANOVA model (score= subgroup\_indicator + treatment + BTX stratum + age group + interaction subgroup \* treatment + centre) or rank ANCOVA model (change = baseline + subgroup\_indicator + treatment + BTX stratum + age group + interaction subgroup \* treatment + centre).

Following contrast analyses for reporting will be performed in case the p-value from the interaction term is deemed statistically significant (lower than 0.1):

- i. The Least Square Mean (LSMeans) of change from baseline in each subgroup, for each treatment group separately, together with its 95% CI,
- ii. Difference in LSMeans in each subgroup between each active dose and Dysport 2 U/kg, together with its 95% CI and the p-value of the test  $H_0$ :Adjusted MeanDysport (8 and 16 U/kg) = Adjusted MeanDysport 2 U/kg.

The ANOVA or ANCOVA models will only be run if there are at least 20 subjects in at least one treatment group. 20 subjects was deemed to be a reasonable number of subjects in order for the analyses to be considered to be meaningful rather than being calculated using any formal statistical methodology.

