11.5 Subgroup Analyses

- Analysis on the primary and first secondary efficacy endpoints will be performed on the randomisation stratification factors i.e. age range and BTX status at baseline (naïve versus non-naïve) and on gender.
- Analysis on the MAS and PGA at Treatment 1 Week 6 and 16 will be performed according to physiotherapy/occupational therapy status at Treatment 1 Week 16 (subjects without physiotherapy nor occupational therapy before week 16 of treatment 1 versus subjects with physiotherapy and/or Occupational therapy without any change in the frequency between baseline and Week 16 of treatment 1).

Additional subgroup analyses may be performed according to clinical interest.

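### The SAP models the physiotherapy/occupational therapy subgroup at Week 16 only and without the protocol's stable-frequency condition, and its visible text does not declare the change

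*SAP*

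**What the plan says.** **Protocol 11.5** names two time points: "Analysis on the MAS and PGA at Treatment 1 Week 6 and 16 will be performed according to physiotherapy/occupational therapy status". The groups are "subjects without physiotherapy nor occupational therapy before week 16 of treatment 1" and "subjects with physiotherapy and/or Occupational therapy without any change in the frequency between baseline and Week 16 of treatment 1". A child whose frequency changed in that period belongs to neither group.

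**SAP 3.2.2.7** places the same subgroup under the single line "MAS and PGA at Treatment Cycle 1 Week 16" and turns it into a No/Yes split. The No group is worded as in the protocol. The Yes side reads "versus subjects with physiotherapy and/or Occupational therapy between Baseline and Week 16 of Treatment Cycle 1", with the frequency condition left out.

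The same SAP section lists the outputs. One is descriptive: "A summary table of raw values and changes from baseline to all visits, by treatment group and overall, in each subgroup separately". The other is a rank ANOVA or ANCOVA with a subgroup-by-treatment interaction; contrasts within subgroups are reported only if the interaction p-value is below 0.1. SAP 3.2.2.6 adds: "Forest plots of effect size by subgroups (Section 3.2.2.7) will also be provided for the primary efficacy endpoint".

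**SAP section 5** lists departures from the protocol down to a change of terminology and the sort order of listings. Its visible text does not mention this subgroup. One entry is redacted.

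**The concern.** The analysis asks whether the dose effect differs between children who do and do not receive therapy. Week 6 is the time point of the primary endpoint and of the PGA secondary endpoint, so that is where a modelled answer would be most useful. The SAP no longer plans one.

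The protocol's condition also kept the therapy group to children with steady therapy. Under the SAP, a child whose sessions were increased or cut after the injection is counted with the steady users. If such changes depend on how a child responded, the split partly reflects the outcome, and the interaction estimate could move in either direction. A reader of the study report who expects the protocol's analysis would find a different one with no visible explanation.

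**Working it through.** No sample size, power or alpha figure is involved, so this is a comparison of text.

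**Step 1. Time points.** The protocol plans analysis at Weeks 6 and 16; the SAP names Week 16 for the model. The SAP's descriptive table covers all visits, so Week 6 means by therapy status will be tabulated. What is lost is the Week 6 interaction model. The forest plot concerns the primary endpoint, which is a Week 6 endpoint, and refers to the whole of 3.2.2.7. It does not say whether the therapy subgroup is included, although that subgroup is listed only for Week 16.

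**Step 2. Who falls where.** Four kinds of child can be told apart. The last column is the alternative proposed under the fix.

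| Therapy course, baseline to Week 16 | Protocol 11.5 | SAP 3.2.2.7 | Baseline status |
|---|---|---|---|
| None throughout | No | No | No |
| Present, frequency unchanged | Yes | Yes | Yes |
| Present at baseline, frequency later raised, lowered or stopped | Neither | Yes | Yes |
| Absent at baseline, started before Week 16 | Neither | Yes | No |

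The documents differ in the third and fourth rows, where the SAP moves the child from excluded to Yes. (Placing the fourth row outside the protocol's groups takes starting therapy to be a change in frequency.)

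**Step 3. How full those rows can be.** Protocol 9.6 says that therapy should not be started from 30 days before baseline up to Week 16, so the fourth row should hold only deviations. It also requires existing therapy to continue at least to Week 16, so complete stopping should be rare. It does not fix the frequency, and it allows school therapy in term time. Changes of frequency, the main part of the third row, are therefore possible without any deviation. Neither document gives a count or an expected proportion.

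**Step 4. When status is known.** Both definitions need information up to Week 16. Applied to a Week 6 outcome, they classify a child partly on events up to 16 − 6 = 10 weeks after that outcome. The protocol definition depends on post-dosing events through the third and fourth rows. The SAP definition depends on them only through the fourth, because a child with therapy at baseline is Yes whatever happens later. Baseline status depends on them in no row.

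**The case against.** The case for the SAP has real substance.

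- For children who follow protocol 9.6, any therapy between baseline and Week 16 is the same as therapy at baseline. The SAP split is then nearly a pre-randomisation one. This stands, with deviations as the exception.
- The protocol definition selects more heavily on what happens after dosing, since it removes every child whose frequency changed. This stands too, and is why simply restoring the protocol wording as the main analysis is not the best remedy.
- Limiting the model to Week 16 avoids classifying a Week 6 outcome by later events. That is a fair reason to drop Week 6 under either document's definition, but the visible text does not give it, and classification at baseline removes the difficulty.
- Baseline status leaves changed-frequency children in the Yes group. Correct; only a supportive analysis under the stable-frequency definition takes them out.

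A reader might infer that the Week 6 result disappears altogether. The all-visits table shows that it does not, and the forest plot may also include it. A reader might also infer that the SAP brings confounding into a comparison that the protocol kept clean. The documents do not support that: therapy is not randomised under either definition, and both use post-randomisation information. Nor can the change be called undeclared without qualification, because section 5 is partly redacted.

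**Conclusion.** The departure is confirmed on both counts: the modelled Week 6 analysis is gone, and the Yes group is wider than the protocol's. The severity is minor. One subgroup analysis is affected, and the primary and secondary tests, the analysis populations and the sample size do not depend on it. The number of children reclassified, and so any effect on the interaction estimate, cannot be derived from the documents.

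This rests on three readings: that the outputs listed in SAP 3.2.2.7 apply to the therapy subgroup as well as to age, BTX status and sex; that the redacted entry in section 5 does not cover this change; and that 9.6 is broadly followed. If the redacted entry does declare it, the complaint about documentation falls away, and the points about definition and time point remain.

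**What to change.** In SAP 3.2.2.7:

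1. Define the subgroup by physiotherapy/occupational therapy status at baseline (Yes/No).
2. Run the interaction model for MAS and PGA at both Week 6 and Week 16.
3. Repeat it with the protocol's stable-frequency definition as a supportive analysis, and summarise changed-frequency children separately so that their number by dose group is visible.

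In SAP 3.2.2.6, state whether the forest plot includes this subgroup. In SAP section 5, record the departure from protocol 11.5 and the reason for it.

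The cost is SAP wording, one or two derived variables and a few added outputs, settled before unblinding. No new data are needed: protocol 7.2 already records the frequency and intensity of therapy at screening, at baseline and at Weeks 2, 4, 6, 12 and 16 of Treatment 1.

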## 1.2 Study Design

This is a phase III, multicentre, double blind, prospective, randomised, controlled multiple treatment study. Subjects will receive a maximum of four treatments over the course of a minimum of one year's study participation.

At study entry, subjects will be randomised into one of the following three treatment groups for Treatment Cycle 1:

- Group A: Dysport 16 U/kg in one upper extremity (the study limb).
- Group B: Dysport 8 U/kg in the study limb.
- Group C: Dysport 2 U/kg in the study limb.

Randomisation will be in a 1:1:1 ratio. Stratification will be performed according to age range (2 to 9 years and 10 to 17 years) and BTX (Botulinum Toxin) naïve or non-naïve status assessed at baseline.

For Treatment Cycles 2, 3 and 4, subjects are planned to receive Dysport 8 U/kg or 16 U/kg according to the treatment allocation by the IRS and will remain double blind throughout the study. However, it is possible that subjects will not receive the planned treatment as dose adaptations (reduction or increase) will be possible based upon the Investigator's judgements regarding safety and efficacy. The total dose for the study limb must not exceed 320 U in the 8 U/kg group and 640 U in the 16 U/kg group.

The planned retreatment interval is 16 weeks and a maximum of four treatments will be administered.

At study entry, a primary targeted muscle group (PTMG), either the elbow flexors or wrist flexors, will be nominated by the Investigator. The PTMG can be changed for subsequent treatments, from elbow to wrist flexors or wrist to elbow flexors, provided that the following criteria are fulfilled:

- The Modified Ashworth Scale (MAS) score of the other muscle group not selected for the last treatment (new PTMG) must be higher than the last treatment PTMG, and
- The new PTMG must have a modified MAS score of greater or equal to 1+.

For Treatment Cycles 2, 3 and 4, injection into the lower extremity/extremities and the nonstudy upper limb will be allowed at the same time as the study limb is injected.

The stages of the study and the planned doses for the study are provided in Figure 1.

Figure 1 Planned Study Structure and Dose Modifications Available During the Study

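### The single subgroup model in SAP 3.2.2.7 enters age group or BTX status twice when that factor is the subgroup; coded as written, the adjusted per-arm subgroup means cannot be estimated

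*SAP*

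**What the plan says.** SAP 3.2.2.7 lists three subgroups for the primary endpoint (MAS) and first secondary endpoint (PGA): "Age group (2 to 9 years and 10 to 17 years"), "BTX status at baseline (naïve or non-naïve") and "Sex (Male or Female"). A fourth, physiotherapy/occupational therapy status, is used at Week 16.

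All of them share one model: subgroup indicator, then "treatment + BTX stratum + age group + interaction subgroup" by treatment, then centre, with baseline added for the MAS change.

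If the interaction p-value is below 0.1, two outputs follow:
- (i) LS means "in each subgroup, for each treatment group separately, together with its 95% CI";
- (ii) the difference of each active dose from 2 U/kg within each subgroup, with CI and p-value.

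Age and BTX status are also the randomisation strata. SAP 1.2 uses the same age cut: "Stratification will be performed according to age range (2 to 9 years and 10 to 17 years"). Protocol 11.5 describes the subgroups as the "randomisation stratification factors i.e. age range and BTX status at baseline".

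The only stated fallback is to drop centre if the model does not converge. On covariates the section says: "Covariates used in models of efficacy analysis will be the same as those mentioned in sections 3.1.1 and 3.1.2". Those two sections name the endpoints and contain no covariates. The covariates are in SAP 3.2.2.1 and 3.2.2.3.

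**The concern.** For sex and therapy status the formula is sound, because the indicator and the two stratum terms are three different variables. For the age and BTX subgroups, the indicator and one stratum term are the same variable.

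An LS mean for one subgroup fixes the indicator at that level but, by default, averages over both levels of every other class effect, including the identical stratum. That describes a child who is in the younger group and also half in each age stratum. No data can inform such a combination, and standard software reports it as non-estimable.

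At stake is output (i) for two of the three subgroups on the primary and first secondary endpoints: the adjusted means by arm, with their confidence intervals, in cases where an interaction has been flagged.

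**Working it through.** The plan gives no figure to reproduce here. This is a question of estimability.

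**Inputs from the documents.** Three arms of 70 (210 children, SAP 1.3.4); the model terms and outputs of SAP 3.2.2.7; two levels each for age, BTX and sex.

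**Assumed.** 20 pooled centres, and LS means with equal weights over the levels of other class effects (the usual default). The algebra in steps 1 and 2 does not depend on the number of centres.

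**1. Per-arm LS means, output (i).** A linear function of the parameters is estimable only if it lies in the row space of the design matrix. If two columns of that matrix are identical, every estimable function must give them the same coefficient. In the age model, the column for indicator level 1 equals the column for age-stratum level 1.
- LS mean for arm *t*, subgroup level 1: indicator weights (1, 0); age-stratum weights (1/2, 1/2).
- For level 1 the coefficients are 1 and 1/2. They differ, so the function is not estimable.
- The same holds for all 2 × 3 = 6 subgroup-by-arm means, and likewise in the BTX model.

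**2. Differences from 2 U/kg, output (ii).** Subtract two LS means at the same subgroup level. The indicator weights become (0, 0), the stratum weights (0, 0), and baseline and centre cancel. Only treatment and interaction weights remain. All 2 × 2 = 4 differences are estimable.

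**3. Numerical check on the 210-child design.** Rank as written for age: intercept 1 + baseline 1 + treatment 2 + indicator 1 + BTX stratum 1 + age stratum 0 (a copy) + interaction 2 + centre 19 = 27. For sex the age stratum adds 1, giving 28.

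| Model | Rank | LS means estimable | Differences estimable |
|---|---|---|---|
| Age or BTX, as written | 27 | 0 of 6 | 4 of 4 |
| Age or BTX, copy removed | 27 | 6 of 6 | 4 of 4 |
| Sex or therapy status | 28 | 6 of 6 | 4 of 4 |

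Removing the copy leaves the differences and the interaction test exactly as they were. For example, the standard error of 16 v 2 U/kg in one age subgroup is 0.27048 residual SDs in both versions. On simulated data the 2-df interaction F is 0.11954 in both for age and 1.05761 in both for BTX.

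**4. If stratum and actual status differ for a few children.** The documents give no count, so these are assumed numbers. The two columns are then no longer identical and the LS means become estimable, but the separation rests on the mismatched children alone. Standard errors in residual SDs:

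| Assumed mismatches | With the extra term | Without it | Ratio |
|---|---|---|---|
| 2 | 0.40–0.42 | 0.16–0.21 | about 2.0–2.5 |
| 3 | 0.33–0.37 | 0.16–0.20 | 0.3299/0.1852 = 1.8 to 0.3532/0.1610 = 2.2 |
| 4 | 0.30–0.33 | 0.16–0.21 | about 1.6–1.9 |

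Overall the inflation is roughly 1.5 to 2.5 times. The standard errors of the dose differences barely change.

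**The case against.** - **The failure depends on coding.** Section 3.2.2.7 gives a formula but no SAS code, and the subgroup indicator is a placeholder. A programmer who uses the stratification variable itself as the indicator would see the repeated effect collapse, and nothing would be lost. Protocol 11.5 makes that natural, since it equates the subgroups with the strata. This stands: the failure is conditional. But the formula names the terms separately, and SAP 4.3 has outputs programmed twice, so the result should not rest on an unwritten choice.
- **The outputs are conditional.** Outputs (i) and (ii) are produced only if the interaction p-value is below 0.1. With no true interaction, that is about a 10% chance per test. This also stands.
- **It would be noticed.** A non-estimable LS mean shows up on the first run; it is not a silent bias. SAP 7.4 allows a departure that is described and justified, and raw values and changes are tabulated by arm in each subgroup regardless. This limits the harm, though it does not make the formula right.
- **Stronger readings.** A reader might infer that the subgroup treatment effects, or the forest plots in SAP 3.2.2.6, are lost. The algebra says otherwise for rank differences. Only if those plots used back-transformed per-arm means would they be touched, and the SAP does not say that the back-transformation of 3.2.2.1 carries over to subgroups. A reader might also take the standard-error ratios as a forecast for this trial. The documents report no mis-stratified children and do not say that stratum and subgroup come from different sources, so the ratios are illustrative only.

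**Conclusion.** The point holds in a limited form. As written, the age and BTX subgroup models contain one factor twice. When the indicator is coded as a separate class variable and matches the stratum for every child, none of the six adjusted per-arm subgroup means can be estimated in either model.

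The loss is confined to output (i), and arises only where the interaction p-value is below 0.1. The rest of the subgroup analysis stands, and so do the primary analysis, its alpha and its power. The estimability result needs only the stated terms and default LS-mean weights. The precision figures under mismatch rest on assumed counts. This is a minor correction, worth making because it is nearly free.

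The faulty covariate reference is a separate small error. It matters here because it is where a programmer would look to settle which terms belong in the model.

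**What to change.** Add to SAP 3.2.2.7: when the subgroup is age group or BTX status, the subgroup indicator replaces the corresponding stratification term. For MAS the two models become:
- age: change = baseline + age group + treatment + BTX stratum + age group × treatment + centre;
- BTX: change = baseline + BTX status + treatment + age group + BTX status × treatment + centre.

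For PGA, use the same terms without baseline. Keep both stratum terms for sex and therapy status. State whether age group and BTX status are taken as randomised or as actual. Change the covariate reference from 3.1.1 and 3.1.2 to 3.2.2.1 and 3.2.2.3.

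The cost is a few lines of SAP text and one term fewer in the age and BTX model statements. Where stratum and status agree for every child, the dose differences and the interaction test do not change.

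### Adjusted subgroup differences are reported only if the interaction p-value is below 0.1, and the unconditional primary-endpoint forest plot has no stated source of estimates

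*SAP*

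**What the plan says.** SAP 3.2.2.7 covers three factors (age group, BTX status, sex) for MAS and PGA at Week 6, and one factor (physiotherapy/occupational therapy status) for "MAS and PGA at Treatment Cycle 1 Week 16". For each it specifies a rank ANOVA or rank ANCOVA with a subgroup-by-treatment term.

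Two kinds of output follow.

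- **Always produced:** "A summary table of raw values and changes from baseline to all visits, by treatment group and overall, in each subgroup separately".
- **Conditional:** "Following contrast analyses for reporting will be performed in case the p-value from the interaction term is deemed statistically significant (lower than 0.1"). This covers the adjusted means by arm in each level, and "Difference in LSMeans in each subgroup between each active dose and Dysport 2 U/kg, together with its 95% CI and the p-value of the test" of no difference.

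A separate rule concerns whether the model is fitted at all: "The ANOVA or ANCOVA models will only be run if there are at least 20 subjects in at least one treatment group". It does not depend on the interaction result.

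SAP 3.2.2.6 then says: "Forest plots of effect size by subgroups (Section 3.2.2.7) will also be provided for the primary efficacy endpoint". No condition is attached, and effect size is not defined.

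Protocol 11.5 has no interaction condition: "Analysis on the primary and first secondary efficacy endpoints will be performed on the randomisation stratification factors i.e. age range and BTX status at baseline", and also by sex. SAP section 5, which lists changes from the protocol, does not mention adding one.

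**The concern.** Subgroup analyses of this kind show whether the effect is consistent across age, prior toxin exposure and sex. Readers judge that from estimates and intervals. An interaction test in a trial sized for main effects has little power, so making the estimates depend on it has two consequences.

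- When the threshold is missed, the reader gets a non-significant interaction p-value and no adjusted interval, which is easily misread as evidence of consistency.
- When it is met, the differences shown have been selected for looking unlike each other.

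There is also a practical gap. The forest plot is promised whatever the interaction p-value, and it points to 3.2.2.7. The only between-arm difference with an interval in that section is the conditional one. The programmer is not told what to plot when the condition fails.

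**Working it through.** **The plan's own figure.** SAP 1.3.4 gives 99% power on each of two endpoints and 98% jointly: 0.99 × 0.99 = 0.9801, which agrees. The effect sizes and SDs behind the 99% are redacted, so an effect size has to be assumed in steps 2 to 4.

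**1. No true interaction (no effect size needed).** Each test falls below 0.1 with probability 0.10.

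- Primary endpoint, three factors: P(none passes) = 0.9³ = 0.729; P(at least one) = 0.271. These treat the tests as independent.
- All eight analyses (3 factors × 2 endpoints at Week 6, plus 1 factor × 2 endpoints at Week 16): P(at least one) = 1 − 0.9⁸ = 0.570. Independence is rougher here because MAS and PGA are correlated.
- Primary-endpoint differences the forest plot could use: 3 factors × 2 levels × 2 doses = 12. Expected number available under the condition: 0.10 × 12 = 1.2.
- Over all eight analyses: 8 × 2 × 2 = 32 differences, of which 3.2 are expected.

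**2. Range for the assumed effect.** With 70 per arm, in SD units and two-sided tests:

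- 99% power for one pairwise comparison: d = (z₁₋α/₂ + 2.326) × √(2/70). At α = 0.05, (1.960 + 2.326) × 0.169 = 0.72. At α = 0.025, (2.241 + 2.326) × 0.169 = 0.77.
- The sample-size text speaks of any tested dose. With equal effects in both doses and a shared control (correlation 0.5), 99% power for at least one significant comparison needs d = 0.62 at α = 0.05 or 0.67 at α = 0.025.

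The range used is therefore 0.62–0.77.

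**3. How often the condition is met when effects do differ.** Assume 35 subjects per arm in each level, normal data, effect d at both doses in one level and d(1 − f) in the other. The interaction F-test has 2 and 3 × 70 − 6 = 204 df (other covariates ignored) and a critical value of 2.33 at 0.10. Its non-centrality is λ = (2/3)(fd)² ÷ (1/35 + 1/35) = 11.67(fd)².

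| d (SD) | Halved (f = 0.5): λ, P(met) | Absent (f = 1): λ, P(met) |
|---|---|---|
| 0.62 | 1.12, 23% | 4.48, 58% |
| 0.72 | 1.51, 28% | 6.05, 70% |
| 0.77 | 1.73, 30% | 6.92, 75% |

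Simulation at d = 0.72 (4,000 trials per setting) gave 27% and 71% with equal levels, and 25% and 63% when the level with the weaker effect held 30% of subjects.

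**4. Size of the selection.** In the same simulation with no true interaction, the mean absolute gap between the two levels' 16 versus 2 U/kg effects was 0.27–0.30 SD over all trials. It was 0.55–0.58 SD among trials that met the condition. The apparent heterogeneity roughly doubles.

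**The case against.** A reader might infer that SAP 3.2.2.6 and 3.2.2.7 cannot both be followed. The text does not establish that. The interaction model is fitted whatever its p-value, so plot estimates could be taken from it, with the contrast tables added only when p < 0.1. Effect size is undefined, and the table and figure indexes that might settle it are redacted. What stands is that no unconditional source is named. The SAP can write a conditional plot when it means one: the centre-by-treatment plots in 3.2.2.2 are expressly conditional.

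A reader might also infer that nothing is shown by subgroup unless the interaction is significant. That is wrong too. Raw summaries by arm are always tabulated, and SAP 3.2.15 gives means a 95% CI. Raw differences can be worked out from these, but the adjusted difference and its interval cannot.

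The two complaints also limit each other. If the forest plot is always produced from the model, selection largely disappears for MAS at Week 6. It then bites on PGA and on the Week 16 therapy-status analyses.

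Finally, the 0.1 rule is prespecified, matches the treatment-by-centre rule and limits unadjusted subgroup p-values. That is a fair reason to be sparing with p-values, but not to withhold intervals.

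**Conclusion.** The point holds as a reporting weakness in supportive analyses. Adjusted subgroup differences and their intervals depend on a low-powered test, and the primary-endpoint forest plot lacks a stated source of estimates.

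The 73% figure for the three primary-endpoint factors rests only on the 0.1 threshold and independence. The 23–30% and 58–75% figures also rest on the assumed effect range, normal data and equal subgroup sizes; the actual models use ranks of ordinal scores. The low-power conclusion for a halved effect is the same across the whole range.

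The documents do not support calling this a proven contradiction, and nothing here affects the primary test, its alpha or the sample size. The change is worth making because the models concerned are already planned.

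**What to change.** In SAP 3.2.2.7, delete the p < 0.1 condition. For every subgroup model that is run, report each dose's LS mean difference from 2 U/kg with its 95% CI in every level, put the interaction p-value beside it, and label the set as exploratory.

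In SAP 3.2.2.6, state that the primary-endpoint forest plot uses these estimates and give their scale: rank, or back-transformed as in SAP 3.2.2.1. If back-transformed, say how the interval is obtained, because 3.2.2.1 describes a back-transformed difference and p-value but no interval for that difference. Also state what the plot shows for a factor whose model is not run under the 20-subject rule.

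The cost is SAP wording, a few more output tables, and more unadjusted subgroup intervals that must be read with caution. No additional subjects, data or alpha are needed.
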